Activity against *Aspergillus* spp.

The *in vitro* activity of SCY-078 has been evaluated against >150 clinical *Aspergillus* isolates, including most clinically relevant species and azole-resistant strains. The results demonstrated potent activity of SCY-078 against all of the strains tested.

Murine models of invasive fungal infections

The antifungal efficacy of SCY-078 has been evaluated in several murine models of disseminated candidiasis and aspergillosis. In a disseminated *C. albicans* model, SCY-078 was more active than fluconazole at all doses. Murine models of SCY-078 in disseminated candidiasis caused by *C. glabrata* and *C. tropicalis* indicated activity across multiple *Candida* species. The SCY-078 area under the concentration-time curve (AUC) in plasma necessary to achieve target efficacy in these models was estimated to be $15.4 \pm 2.2 \mu\text{M}\cdot\text{hr}$.

Nonclinical experience

Toxicology studies in rats and dogs have been conducted with SCY-078 following oral administration for up to 90 days. The results from the non-clinical safety program are supportive of the doses and treatment duration intended in this study.

The *in vitro* studies indicated that SCY-078 metabolism was predominantly oxidative, with cytochrome P450 (CYP) 3A being the primary enzyme involved in its oxidative metabolism. Strong inhibitors of CYP3A would be expected to increase plasma levels of SCY-078; therefore, the concurrent administration of SCY-078 with such inhibitors is prohibited.

Clinical experience

To date, over 300 subjects and patients have received either oral or IV formulations of SCY-078 in Phase 1 and Phase 2 studies.

SCY-078 was generally well tolerated following single oral doses of up to 1600 mg and multiple oral doses of up to 800 mg/day for 28 consecutive days in Phase 1 studies. Reported adverse events (AEs) after oral administration have been generally transient and primarily mild to moderate in intensity. The most frequently reported AEs have been mild gastrointestinal events (nausea, vomiting, diarrhea and abdominal pain).

A Phase 2 study of oral SCY-078 as step-down therapy from IV echinocandin in patients with invasive candidiasis has been completed. Following three to ten days of IV echinocandin therapy, 21 patients received either SCY-078 or fluconazole. SCY-078 was well tolerated, with an AE profile typical of this population and comparable to the SOC. The results from this study also

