indicated that the higher dose of SCY-078 tested (750 mg QD) is predicted to achieve the target exposure at steady state in the majority of patients.

A Phase 2 proof-of-concept study of oral SCY-078 in patients with acute vulvovaginal candidiasis (AVVC) has also been completed. In this multicenter, randomized, active-controlled, evaluator-blinded study of oral SCY-078 compared to oral fluconazole in adult female patients with AVVC, 96 patients with an acute, moderate to severe, symptomatic episode of vulvovaginal candidiasis were randomized in a 1:1:1 ratio to receive either oral SCY-078 750 mg with a 1250 mg loading dose for three days, oral SCY-078 750 mg with a 1250 mg loading dose for five days or a single dose of oral fluconazole. SCY-078 was well tolerated, with the most common AEs being mild gastrointestinal events. The high clinical cure rates observed in this study are supportive of the clinically relevant antifungal activity of SCY-078 in this form of *Candida* infection.

Several drug-drug interaction studies have been conducted. Ketoconazole (a strong inhibitor of CYP3A) induces a significant (5-fold) increase in SCY-078 exposure, while diltiazem (a moderate inhibitor of CYP3A) induces a mild to moderate (<3-fold) increase in SCY-078 exposure. SCY-078 did not have any effect on rosiglitazone (a CYP2C8 substrate) exposure, had only a mild effect (less than a 0.5-fold increase) on the AUC of tacrolimus (a CYP3A and P-glycoprotein [P-gp] substrate) and had no effect on the maximum concentration (C_{max}) of tacrolimus.

SCY-078 has the potential to be an important addition to the antifungal treatment arsenal by providing potent activity against the full spectrum of *Candida* species, including difficult-to-treat organisms, and by affording the added flexibility of both oral and IV formulations.

For additional information on SCY-078, please refer to the Investigator's Brochure (IB).

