11.2 Exclusion Criteria

A subject will be excluded from participation in the study if she meets any of the following exclusion criteria:

1. Subject has any vaginal condition other than AVVC that may interfere with the diagnosis or evaluation of response to therapy, such as suspected or confirmed concurrent causes of vulvovaginitis and/or cervicitis including bacterial vaginosis, *Trichomonas*, active *Herpes* virus, *N. gonorrhoea*, *Chlamydia*, active human papillomavirus or other mixed infections.
2. Subject requires treatment with the prohibited medications (including prescription and over-the-counter medications, supplements, and herbal products) listed in [Section 21.0 \(Appendix A\)](#), during the following timeframes:
 - a. Systemic and/or topical (vaginal) antifungal treatment, including prescription or over-the-counter products, within 28 days prior to enrollment if administered for the treatment of VVC and during the study for all cases
 - b. CYP3A4/5 inducers and strong time-dependent CYP3A4/5 inhibitors during the 14 days prior to enrollment and during study treatment
 - c. Strong or moderate reversible CYP3A4/5 inhibitors, including azoles and grapefruit juice, during 48 hours prior to enrollment and during study treatment until TOC

- d. Select CYP2C8 substrates during the 48 hours prior to enrollment or during study treatment
 - e. Select P-gp substrates during the 48 hours prior to enrollment or during study treatment SCY-078
3. Subject is actively menstruating at the time of the Baseline visit.
 4. Subject has uncontrolled diabetes mellitus.
 5. Subject has a vaginal sample with pH >4.5.
 6. Subject has a history of or an active cervical/vaginal cancer.
 7. Subject has a known hypersensitivity to SCY-078, fluconazole or any of the components of the formulation.
 8. Subject has a known human immunodeficiency virus infection and/or is receiving chemotherapy or has an illness that, in the judgment of the investigator, is serious enough to induce an immune deficiency.
 9. Subject has had any major illness within 30 days before Screening.
 10. Subject is pregnant or lactating.
 11. Subject has participated in any other investigational study within at least 30 days (or 5.5 half-lives of the investigational product) before signing the ICF.
 12. Subject has received prior treatment with the study drug in a previous trial.

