12.2 Dietary Requirements

For all treatment groups, oral study drug must be administered 30 minutes before or 2 hours after any meal and must be taken with approximately 8 oz./240 mL of water.

Nutraceuticals and foods that are known CYP3A inhibitors, such as grapefruit juice, blood oranges and mulberry juice should not be consumed until the last PK sample is collected (TOC) (see [Section 21.0 \[Appendix A\]](#)).

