13.4 Study Restrictions

There are no additional study restrictions other than those described in [Sections 11.2](#) (Exclusion Criteria), [Section 12.2](#) (Dietary Requirements) and [Section 13.2](#) (Prohibited Medications).

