14.14 Study Drug Dosing

Study drug doses will be self-administered by the subjects from Baseline (Day 1) through Day 3. Details of study treatment groups and dietary requirements for treatment administration are provided in [Section 12.1](#) and [Section 12.2](#), respectively.

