21.0 Appendices

Appendix A: Prohibited Medications and Medications to be Administered with Caution

Prohibited Medications

The use of any topical vaginal corticoids and contraceptives is prohibited during the study. No antifungal treatment other than the study drug is allowed during the study. In addition, the medications listed below are also prohibited.

Strong CYP3A4/5 inhibitors and CYP3A4/5 inducers

CYP	Strong Inhibitors	Moderate Inhibitors	Inducers ^a
3A4/5	Reversible inhibitors^b 
 • boceprevir • conivaptan • indinavir • itraconazole^c • ketoconazole^c • lopinavir/ritonavir • mibefradil 	Reversible inhibitors^b 
 • fluconazole^c 	
 • avasimibe • carbamazepine • phenytoin • rifampin • St. John's wort
	Time-dependent inhibitors^a 
 • clarithromycin • ritonavir • saquinavir 		

- a. The CYP3A4/5 inducers and strong time-dependent CYP3A4/5 inhibitors listed in this table are not permitted during the 14 days prior to enrollment and during study treatment.
- b. The strong and moderate reversible CYP3A4/5 inhibitors listed in this table are not permitted during the 48 hours prior to enrollment and during study treatment.
- c. No antifungal treatment other than the study drug is allowed during the study.

CYP2C8 substrates

CYP	Substrates
2C8 ^a	amiodarone, amodiaquine, paclitaxel, repaglinide, montelukast, pioglitazone and rosiglitazone,

- a. The CYP2C8 substrates listed in this table are not permitted during the 48 hours prior to enrollment or during study treatment.

P-glycoprotein (P-gp) substrates

P-gp Drug Substrates ^a
digoxin, colchicine

- a. The P-gp substrates listed in this table are not permitted during the 48 hours prior to enrollment or during study treatment

Medications to be administered with Caution and Monitored as Appropriate

CYP	Moderate Inhibitors
3A4/5	Reversible inhibitors^a 
 • amprenavir • aprepitant • atazanavir • buprenorphine • ciprofloxacin • crizotinib • cyclosporine 
 • darunavir/ritonavir • fosamprenavir • imatinib • grapefruit juice, blood oranges, mulberry juice
	Time-dependent inhibitors: 
 • diltiazem • erythromycin • verapamil

CYP3A4 substrates

CYP	Substrates

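### Protocol Appendix A places three CYP3A-inhibiting foods in the use-with-caution table, while Section 12.2 bars all three until TOC and exclusion 2c bars grapefruit juice by name

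*Protocol*

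**What the plan says.** **Foods.** The caution part of Protocol Appendix A lists "grapefruit juice, blood oranges, mulberry juice" as moderate reversible CYP3A4/5 inhibitors. They do not appear in the prohibited table, where the only moderate inhibitor is fluconazole. Section 13.2 refers to Appendix A for the complete prohibited list. Section 13.3 refers to it for the complete caution list, and allows moderate inhibitors with caution apart from the selected prohibited ones.

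Section 12.2 states the opposite rule for the same three items: "grapefruit juice, blood oranges and mulberry juice should not be consumed until the last PK sample is collected (TOC". It then refers the reader to Appendix A. Exclusion 2c in Section 11.2, repeated in the Synopsis, names grapefruit juice: "Strong or moderate reversible CYP3A4/5 inhibitors, including azoles and grapefruit juice, during 48 hours prior to enrollment and during study treatment until TOC". Section 13.4 says "There are no additional study restrictions other than those described in" Sections 11.2, 12.2 and 13.2, so the dietary rule is a binding restriction.

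**End date.** Footnote b of the prohibited table says that the "strong and moderate reversible CYP3A4/5 inhibitors listed in this table are not permitted during the 48 hours prior to enrollment and during study treatment". It does not mention TOC. Section 14.14 gives the dosing period: "Study drug doses will be self-administered by the subjects from Baseline (Day 1) through Day 3".

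**The concern.** Appendix A is the page a site would consult when a subject asks about a drug or food. On the three foods it gives the opposite answer to Section 12.2, and for grapefruit juice the opposite answer to an exclusion criterion. Section 12.2 itself sends the reader there.

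The protocol has a pharmacological reason for the ban. Section 7.1 identifies CYP3A as the primary enzyme in the oxidative metabolism of SCY-078 and adds that "Strong inhibitors of CYP3A would be expected to increase plasma levels of SCY-078". It reports that "Ketoconazole (a strong inhibitor of CYP3A) induces a significant (5-fold) increase in SCY-078 exposure", and that diltiazem, a moderate inhibitor, gives a rise of less than 3-fold. Appendix A classes the three foods as moderate inhibitors. Intake during dosing or PK sampling could add noise to the exposure data, in a study that plans to relate exposure to clinical cure (Section 18.6.2).

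A second consequence is inconsistent deviation calls. SAP Section 7 gives eligibility violations and interfering concomitant medication as examples of major deviations that remove a subject from the per-protocol population. Sites working from different pages could report the same intake differently.

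**Working it through.** No sample-size, power or error-rate figure is involved. The check is a comparison of texts plus simple date arithmetic.

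**1. The foods, side by side**

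| Source (Protocol) | Grapefruit juice | Blood oranges | Mulberry juice | Period |
|---|---|---|---|---|
| Appendix A, prohibited table | absent | absent | absent | none |
| Appendix A, caution table | with caution | with caution | with caution | none visible |
| Section 12.2 | barred | barred | barred | until TOC |
| Exclusion 2c (Section 11.2, Synopsis) | barred by name | not named | not named | 48 hours before enrollment until TOC |

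All three foods conflict with Section 12.2. Grapefruit juice also conflicts with 2c.

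**2. Which rule governs.** Section 12.2 is the dedicated dietary section, Section 13.4 names it as a source of restrictions, and 2c supports it for grapefruit juice. A site that applies the strict rule breaches no other text. The Appendix A entry is therefore the one to correct, subject to the footnote that cannot be seen.

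**3. The end-date difference**
- Last dosing day: Day 3 (Section 14.14).
- TOC: Day 10 ± 2, so Day 8 to Day 12 (Section 15.0, Table 2).
- Difference between the end of study treatment and TOC: 8 − 3 = 5 days at least, 10 − 3 = 7 days nominally, 12 − 3 = 9 days at most.

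**4. Drugs to which footnote b's shorter wording matters**
- Strong reversible inhibitors in the prohibited table: boceprevir, conivaptan, indinavir, itraconazole, ketoconazole, lopinavir/ritonavir, mibefradil = 7.
- Footnote c bars antifungals throughout the study. That removes itraconazole and ketoconazole: 7 − 2 = 5.
- The one moderate inhibitor listed, fluconazole, is also covered by footnote c: 1 − 1 = 0.
- The nominal total is 5 drugs. Two of them, indinavir and lopinavir/ritonavir, are antiretrovirals, and exclusion 8 removes known HIV infection.

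**5. Ceiling on PK subjects.** The PK Subset has 10 subjects per group, and only SCY-078 samples are analysed (Section 10.1.2): 5 arms × 10 = 50. The documents do not say how many would consume these foods or start one of these drugs.

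**6. Size of any exposure change.** Section 7.1 gives figures only for ketoconazole and diltiazem. It gives none for the three foods, and none for inhibitor use after the last dose.

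**The case against.** The strongest reply is that the operative rules are already clear and only a table entry is out of line. Section 12.2 bars the foods outright, Section 13.4 gives that section force, and 2c names grapefruit juice. This is right about which rule governs. It does not remove the conflict, because Sections 12.2, 13.2 and 13.3 all direct the site to the table that says otherwise.

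A second reply concerns the table itself. The superscript a on the caution-table heading attaches to the very group that holds the foods, and its footnote cannot be seen. It may restrict those entries. Text lost in extraction is not an error in the plan, so the food point carries this caveat.

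The third reply concerns footnote b. A reader might infer that it ends the ban on Day 3 and permits these inhibitors afterwards. The documents do not support that. The lead-in to criterion 2 takes the list of medications from Appendix A but sets its own timeframes in items a to e. Footnote b prints no day and grants no permission; it is silent on the days after treatment, and 2c covers them. What remains is an omission to align.

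Two other stronger readings also fail:
- A reader might take 50 as the number of subjects at risk. It is only the number whose samples are to be analysed.
- A reader might conclude that food intake could never be traced. Section 14.15 describes no food item in the diary. But Section 13.1 has supplements and herbal products recorded, and SAP Section 11.2 has protocol deviations logged, so intake could still come to light.

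**Conclusion.** The point holds as a minor internal inconsistency in the operating instructions. It is not a flaw in the design. Appendix A, as visible, allows with caution three foods that Section 12.2 bars until TOC, one of which 2c also bars. The shorter wording of footnote b is a secondary mismatch that criterion 2 overrides.

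The effect cannot be quantified from the documents and is probably small:
- The primary mITT analysis is unaffected: mITT membership depends only on the KOH test and culture, and the test does not change.
- PK is an exploratory objective (Section 8.3).
- The population PK model pools other oral studies and predicts Day 1 AUC and Cmax (Section 18.6.2). Inhibitor intake after Day 3 cannot alter Day 1 exposure. In Groups 1 to 3, active SCY-078 is given on Day 1 only.
- Intake of the foods during dosing is the case that could matter for exposure, in an unknown number of subjects. For the PK data the ceiling is about 50.

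The verdict assumes that the footnote behind superscript a does not already bar the foods. If it does, the food point reduces to a misplaced entry. The footnote b point does not depend on it.

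**What to change.** Two edits in Appendix A:

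(a) Remove grapefruit juice, blood oranges and mulberry juice from the caution table. List them in Appendix A as not to be consumed until TOC, with the 48-hour look-back before enrollment for grapefruit juice, as in 2c. Check the footnote to superscript a in the full document at the same time.

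(b) In footnote b, add *until TOC* after the reference to study treatment, so that it matches 2c.

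Criterion 2c and Section 12.2 need no change. The cost is wording only, by clarifying amendment or site memo. No procedure, visit, data field or analysis is added.

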10.1.1 Study Visits

Screening (Day -1)

Consenting subjects who are experiencing vulvovaginal symptoms at Screening will be evaluated by the investigator, who will obtain a vaginal sample for local KOH testing and for fungal culture and species identification by the central laboratory. Susceptibility testing will be done at the central laboratory for all positive cultures for *Candida* spp. Additional vaginal samples will be collected, if clinically indicated, to be examined for the presence of other pathogens (e.g., causative agents for bacterial vaginosis, *Trichomonas*, *Herpes* virus, *N. gonorrhoea*, *Chlamydia*, human papillomavirus or other mixed infections) by a qualified laboratory (central or local laboratory) and for the determination of vaginal pH by the investigator. The investigators and the subjects will rate the signs (edema, erythema and excoriation) and symptoms (itching, burning and irritation) of infection, respectively, on a standardized vulvovaginal signs and symptoms scale (the Vulvovaginal Signs and Symptoms [VSS] Scale) (see [Appendix B](#)). Safety procedures, including an abbreviated physical exam, vital signs, laboratory tests and a pregnancy test will also be performed.

To be eligible for inclusion, subjects must have a minimum composite score of vulvovaginal signs and symptoms ≥ 7 with at least 2 signs or symptoms having a score of 2 (moderate) or greater in the VSS Scale, a positive KOH test and a normal vaginal pH (≤ 4.5).

Baseline (Day 1)

At the Baseline visit (which may be combined with the Screening visit), eligible subjects will be randomized in equal allocation (at a 1:1:1:1:1:1 ratio) to one of the following 6 active treatment groups (5 experimental groups and 1 active comparator group):

- Treatment Group 1: oral SCY-078 750 mg QD on Day 1 only
- Treatment Group 2: oral SCY-078 300 mg BID on Day 1 only
- Treatment Group 3: oral SCY-078 450 mg BID on Day 1 only
- Treatment Group 4: oral SCY-078 150 mg BID on Days 1 to 3
- Treatment Group 5: oral SCY-078 300 mg BID on Days 1 to 3
- Treatment Group 6: oral fluconazole 150 mg QD on Day 1 only

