12.0 Study Treatments

Subjects who meet all of the inclusion and none of the exclusion criteria will be enrolled into the study and will be randomized in equal allocation (at a 1:1:1:1:1:1 ratio) to one of the following 6 active treatment groups of the study (5 experimental groups and 1 active comparator group):

- Treatment Group 1: oral SCY-078 750 mg QD on Day 1 only
- Treatment Group 2: oral SCY-078 300 mg BID on Day 1 only
- Treatment Group 3: oral SCY-078 450 mg BID on Day 1 only
- Treatment Group 4: oral SCY-078 150 mg BID on Days 1 to 3
- Treatment Group 5: oral SCY-078 300 mg BID on Days 1 to 3
- Treatment Group 6: oral fluconazole 150 mg on Day 1 only

For the purpose of maintaining treatment blinding, all randomized subjects will receive matching SCY-078 placebo tablets and/or matching fluconazole placebo capsules as needed based on treatment assignment, in a double-dummy fashion. A summary of dose levels, dosing days, total daily dose, tablet strength and tablet quantity for each treatment group is provided in Table 1.

Table 1: Study Treatment Groups (Study SCY-078-204)

Treatment Group	Dose Level	Dosing Day			Total Daily Dose	Strength/Number of Tablets/Capsules per Dose
		Day 1	Day 2	Day 3		
Group 1	SCY-078 750 mg	QD			SCY-078 750 mg	150-mg tablet/5 tablets
Group 2	SCY-078 300 mg	BID			SCY-078 600 mg	150-mg tablet/2 tablets
Group 3	SCY-078 450 mg	BID			SCY-078 900 mg	150-mg tablet/3 tablets
Group 4	SCY-078 150 mg	BID	BID	BID	SCY-078 300 mg	150-mg tablet/1 tablets
Group 5	SCY-078 300 mg	BID	BID	BID	SCY-078 600 mg	150-mg tablet/2 tablets
Group 6 (comparator)	FLU 150 mg	QD			FLU 150 mg	150-mg capsule/1 capsule

Abbreviations: BID = twice daily; FLU = fluconazole; QD = once daily

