12.3.2 Formulation, Packaging and Labelling

SCY-078 citrate drug product for oral administration will be supplied as a tablet containing 150 mg of SCY-078 active ingredient on a free-base basis. In addition to the active ingredient, the tablet formulation also contains silicified microcrystalline cellulose, crospovidone, mannitol, colloidal silicon dioxide, magnesium stearate (non-bovine) and butylated hydroxyanisole.

Fluconazole study drug will be sourced commercially and will be modified (encapsulated) for the purpose of blinding. Fluconazole will be provided as a capsule containing 150 mg of active ingredient.

Study drug supplies will be packaged in a treatment kit, a box containing bottles (active drug plus matching placebo), for all three study treatment days (Days 1-3).

Bottles will contain the following active treatment:

- Treatment Group 1: 5 tablets of SCY-078
- Treatment Group 2: 4 tablets of SCY-078
- Treatment Group 3: 6 tablets of SCY-078
- Treatment Group 4: 6 tablets of SCY-078 (2 tablets each for Day 1, Day 2 and Day 3)
- Treatment Group 5: 12 tablets of SCY-078 (4 tablets each for Day1, Day 2 and Day 3)
- Treatment Group 6: 1 capsule of fluconazole

For the purpose of blinding, the number and appearance of dosage units will be the same across all treatment groups, as follows:

- Day 1: 5 tablets for the morning dose + 3 tablets and 1 capsule for the evening dose

- Day 2 and Day 3: 2 tablets for the morning dose + 2 tablets for the evening dose

Labels on the kits and/or bottles containing study medication will include the following information and any other information required by applicable regulations:

- Sponsor Name
- Study Protocol Number
- Place to write the subject number
- Number of tablets/capsules count per bottle or box
- Dosing instructions
- Storage conditions
- Caution Statement: "Caution: New Drug – Limited by Federal (United States) Law to Investigational Use Only"

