3A4	
In vitro, SCY-078 was an inhibitor of CYP3A mediated metabolism of midazolam, but was only a weak inhibitor of metabolism of testosterone. The clinical significance of this inhibition is unknown; caution should be exercised when administering SCY-078 with drugs known to be CYP3A sensitive substrates with narrow therapeutic index.
 
Subjects receiving sirolimus, tacrolimus or warfarin are permitted for enrollment in the study and these medications may be administered concomitantly with SCY-078 with close monitoring. The administration of either sirolimus or tacrolimus should be offset by no less than 2 hours with the administration of SCY-078. At a minimum, blood levels of sirolimus, tacrolimus or PT/PTT/INR for subjects on warfarin should be measured after the first dose of SCY-078 and when the subject has received approximately 7 days of SCY-078 (at which time, SCY-078 concentrations will have reached steady state). Dosing adjustments and subsequent monitoring of sirolimus and warfarin should be undertaken in accordance with product prescribing information for the respective agents.

Abbreviations: PT = prothrombin time; PTT = partial thromboplastin time; INR = international normalized ration

OATP1B3 substrates

OATP	Substrate
1B3	
In vitro, SCY-078 is an inhibitor of the OATP1B3 liver uptake transporter. The clinical significance of this inhibition is unknown; however, there is a potential risk for increased exposure of the concomitant medications (arising from lowered hepatic clearance) when administering SCY-078 with drugs known to be OATP1B3 selective substrates. Therefore, caution should be exercised when administering SCY-078 with drugs known to be OATP1B3 selective substrates such as telmisartan, including monitoring the subject for signs of overexposure associated with the concomitant medications as described in the product prescribing information.

Sources:

- FDA Draft Guidance for Industry. Drug Interaction Studies – Study Design, Data Analysis, and Implications for Dosing and Labeling. 2012.
- Drug interactions in infectious disease by Stephen C. Piscitelli, Keith Rodvold (2007)
- UCSF-FDA Transportal

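### Protocol Appendix A ties the second minimum check for sirolimus, tacrolimus and warfarin users to about 7 days of SCY-078, which no arm receives

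*Protocol*

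**What the plan says.** The CYP3A4 substrate table in Protocol Appendix A allows users of sirolimus, tacrolimus or warfarin into the study under close monitoring. It sets two checks as a minimum: the level of sirolimus or tacrolimus, or PT/PTT/INR for warfarin.

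- First check: these "should be measured after the first dose of SCY-078".
- Second check: due "when the subject has received approximately 7 days of SCY-078", with the reason "at which time, SCY-078 concentrations will have reached steady state".

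The next sentence sends dose adjustment and later monitoring of sirolimus and warfarin to their prescribing information. It does not name tacrolimus.

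The dosing sections give much shorter courses. Protocol 10.1.1 lists, for example, "Treatment Group 3: oral SCY-078 450 mg BID on Day 1 only". The longest SCY-078 courses are those of Groups 4 and 5; Protocol 12.0 gives "Treatment Group 5: oral SCY-078 300 mg BID on Days 1 to 3". Protocol 14.14 closes dosing for everyone: "Study drug doses will be self-administered by the subjects from Baseline (Day 1) through Day 3".

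**The concern.** The second check is counted in days of SCY-078 received and justified by steady state. If no regimen lasts that long, one of the two stated minimum safety checks has no time point at which it can be done. The drugs concerned have narrow safety margins. Appendix A itself asks for caution with sensitive CYP3A substrates of narrow therapeutic index and says that the clinical meaning of the in vitro inhibition is unknown. Protocol 7.1 reports a mild effect on tacrolimus AUC and none on its Cmax, but gives no result for sirolimus or warfarin.

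What is at stake is the safety monitoring of a small subgroup. No estimate, test or sample-size statement depends on it.

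**Working it through.** **Step 1. Days of SCY-078 in each arm.** The active tablets per kit come from Protocol 12.3.2 and the daily dose from Protocol Table 1 (150 mg tablets). Days = tablets supplied / tablets per day. For Group 5 the supply is stated as "Treatment Group 5: 12 tablets of SCY-078 (4 tablets each for Day1, Day 2 and Day 3".

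| Group | SCY-078 tablets in kit | Tablets per day | Days of SCY-078 | Share of 7 days |
|---|---|---|---|---|
| 1 | 5 | 5 | 5/5 = 1 | 1/7 = 14% |
| 2 | 4 | 4 | 4/4 = 1 | 14% |
| 3 | 6 | 6 | 6/6 = 1 | 14% |
| 4 | 6 | 2 | 6/2 = 3 | 3/7 = 43% |
| 5 | 12 | 4 | 12/4 = 3 | 43% |
| 6 (fluconazole) | 0 | 0 | 0 | 0% |

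The supply agrees with the dosing days in Protocol 10.1.1 and 12.0. The trigger is met in 0 of 5 SCY-078 arms. The word approximately cannot stretch 7 to 3, which is less than half.

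**Step 2. Does a later calendar day satisfy the text?** By study Day 7 the last SCY-078 dosing day is 7 − 1 = 6 days past in Groups 1 to 3 and 7 − 3 = 4 days past in Groups 4 and 5. A sample on that day would follow washout time. It would not follow 7 days of drug, and the steady-state reason would not apply.

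**Step 3. Does anything else supply the check?**

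- The safety panel in Protocol 14.7 covers hematology and chemistry, with no PT, PTT, INR or drug level.
- Protocol Table 2 schedules no such test. INR appears in Protocol 16.3 only as part of a liver-event definition.
- Protocol 13.3 requires caution and appropriate monitoring for these drugs and refers to Appendix A for the list. It sets no time.

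**Step 4. The first check.** This remains workable. Protocol 10.2 blinds the sites, and Protocol 12.3.2 says that "the number and appearance of dosage units will be the same across all treatment groups". A site would therefore apply the check after the first dose to every such subject, including any in Group 6.

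**Step 5. Where a replacement could sit.** Under Protocol 10.1.1 the PK subset (10 per group, 60 of about 180) attends the site on Day 3; all others have a phone contact. SAP 11.11 places the Day 3 post-dose sample after the 5th or 6th of 6 doses. After the 5th dose, Group 4 has taken 5 × 150 = 750 of 900 mg and Group 5 has taken 5 × 300 = 1500 of 1800 mg, which is 5/6 = 83% in both. Groups 1 to 3 finished SCY-078 on Day 1.

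**The case against.** The best defence is that the clause is conditional. If 7 days of SCY-078 never occur, the check is simply not triggered; and because no arm reaches steady state on the document's own account, the stated reason for the check disappears as well. On that view, deleting the clause is as good a correction as re-timing it. Part of this stands: the protocol never promised an end-of-exposure check, and the choice of Day 3 is a recommendation that the documents do not dictate. But the text presents the two checks as a minimum, and a minimum that can never apply is an error whichever way it is repaired.

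The defence is also right about mitigation and numbers. A reader might infer any of the following, and the documents do not support them:

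- *That sites are left with no guidance and must guess or omit monitoring.* The first check, the close-monitoring requirement and Protocol 13.3 still hold, and prescribing information governs later monitoring of sirolimus and warfarin. Only tacrolimus lacks that last reference, and it is the one drug with a reported interaction result, which was mild.
- *That all subjects outside the PK subset (about 180 − 60 = 120) would need an extra draw.* Only users of these three drugs would.
- *That re-timing costs nothing because a draw is already required.* A draw that never falls due is not being replaced, so in practice one is added.
- *That a Day 3 sample always marks the end of dosing.* After the 5th dose one dose remains.

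The TOC visit (Day 10 ± 2) is another candidate, since every subject is on site with blood taken. It needs no extra visit, but it falls between 8 − 3 = 5 and 12 − 3 = 9 days after the last dosing day in Groups 4 and 5.

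**Conclusion.** Wrong as written, and minor. Of the two minimum checks in Appendix A, one can be done as stated and one cannot, in any arm.

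The number of affected subjects is not given and may be zero. Appendix A admits users of these drugs. The requirement for good general health (Protocol 11.1) and the exclusions for immune-compromising illness or unacceptable risk (Protocol 11.2, criteria 8 and 13) probably reduce their number.

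The conclusion rests on reading the trigger as days of SCY-078 actually received, which is how it is worded and what the steady-state reason requires. It does not claim that any subject would be harmed, nor that monitoring would lapse altogether. Efficacy analyses and dose selection are unaffected.

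**What to change.** In Appendix A, delete the trigger based on 7 days and steady state. Require the drug level or PT/PTT/INR at two times: after the first dose of study drug, and on or shortly after Day 3, the last day of blinded dosing. The clinical team should confirm the second day.

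Word both checks by study drug, so that they apply to every subject on sirolimus, tacrolimus or warfarin whatever her blinded arm. This protects the blind. It also covers Group 6, since Appendix A lists fluconazole as a moderate CYP3A4/5 inhibitor.

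Users in the PK subset can have the sample at the on-site Day 3 visit. Other users need a local draw or an unscheduled visit.

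The cost is a wording change in Appendix A and, in practice, one added draw and possibly one added visit for each user of these drugs. Other subjects are not affected.
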